EVALUATION OF THE BIOAVAILABILITY OF METRONIDAZOLE DERMAL PRODUCTS

Short title: PK of metronidazole dermal products

UMB IRB #: HP-00071790

Principal Investigators:

[name] (contact), PhD, RPh (*PI*)

Medically Accountable Investigators:

[name], MS (*primary*)
[name] (*secondary*)

Sponsor:

Food and Drug Administration
Office of Generic Drugs

Grant Number: 1U01FD004947

NCT: NCT03271983

Version 7.0

12 April 2019

STATEMENT OF COMPLIANCE

This trial will be conducted in compliance with the protocol, International Conference on Harmonization Good Clinical Practice E6 (ICH-GCP) and the applicable Food and Drug Administration and other Department of Health and Human Services regulatory requirements.

All key personnel (all individuals responsible for the design and conduct of this study) have completed Human Subjects Protection Training.

PROTOCOL SUMMARY

Title:	Evaluation of the bioavailability of metronidazole dermal products
Population:	Healthy adults age 18 - 45 years
Number of Sites:	Single site: University of Maryland School of Medicine
Study Duration:	Approximately up to 1 year
Subject Participation Duration:	Approximately 10 weeks including the screening period
Description of Study Product:	Metronidazole topical gel, 0.75%, Prasco Laboratories; Metronidazole topical gel, 0.75%, Impax Laboratories; Metronidazole topical cream, 0.75%, Fougera Laboratories.
Objective:	
The present study aims to study the systemic bioavailability of metronidazole in healthy volunteers following the application of topical metronidazole products: metronidazole topical gel, 0.75% (RLD), metronidazole topical gel, 0.75% (generic) and metronidazole topical cream, 0.75% (generic). The metronidazole gel, 0.75% products are therapeutically equivalent. The metronidazole cream, 0.75% will be used as an inequivalent control for the study.
 
The pharmacokinetic data obtained in this study will be used in combination with in vitro data collected elsewhere to develop an in vitro in vivo correlation that could be leveraged to evaluate bioequivalence of generic metronidazole topical drug products.

Description of Study Design:	
The study will be an open-label, crossover study over 10 weeks (n=12 healthy subjects) with one week washout period between studies.
 
The study contain six procedure days:
 
• Procedure Day 1: RLD topical gel containing 0.75% metronidazole to be applied for 25 h. Blood samples obtained on Procedure Day 1 and 2.• Procedure Day 3: Generic topical gel containing 0.75% metronidazole to be applied for 25 h. Blood samples

obtained on **Procedure Day 3 and 4.**

- **Procedure Day 5:** Generic topical cream containing 0.75% metronidazole to be applied for 25 h. Blood samples obtained on **Procedure Day 5 and 6.**

A) *Pharmacokinetics*

Each subject will be his/her own control and each subject will sign an institutional review board–approved consent form explaining the purpose, nature, risks, benefits, and duration of the study. The study will be conducted in accordance with good clinical practice guidelines and with the ethical principles originating in the Declaration of Helsinki.

The subject's skin in the area of application (upper arm) will be relatively free of hair before gel or cream application. Blood samples (approximately 5 mL (1 tsp) each) will be drawn in BD vacutainer tubes. On Procedure Day 1, 2, 3, 4, 5 and 6, blood samples will be obtained as follows:

- Within 60 min pre-gel/cream application and then during wear, up to 25 h.

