1 KEY ROLES

U01 Principal Investigators:

[name] (contact), PhD, RPh (*PI*)
Professor
Department of Pharmaceutical Sciences
University of Maryland School of Pharmacy
[name]
[name]
[contact]
[contact]
Email: [contact]

Medically Accountable Investigators

[name] MD, MS (*primary*)
Professor
Department of Medicine and Epidemiology (*secondary*)
University of Maryland School of Medicine
[name]
[name]
[contact]
[contact]
E-mail: [contact]

[name]. (*secondary*)
University of Maryland School of Medicine
Department of Medicine
Pediatrics
North Hospital
[name]
[contact] or [contact]
Email : [contact]

Schematic of Study Design**n=12 subjects****Study Session 1****[Procedure Day 1 and 2]**

Product: **Metronidazole gel, 0.75% (RLD)**
Time of admission: **Morning of Procedure Day 1**
Time of application: **Morning of Procedure Day 1**
Duration of application: **25 h**
Sampling: **26 hours**
Sampling time points: **-60 min, 1, 2, 3, 4, 5, 6, 7, 8, 9, 10, 23, 24, 25 h**

Washout period at least 1 week

Study Session 2**[Procedure Day 3 and 4]**

Product: **Metronidazole gel, 0.75% (generic)**
Time of admission: **Morning of Procedure Day 3**
Time of application: **Morning of Procedure Day 3**
Duration of application: **25 h**
Sampling: **26 hours**
Sampling time points: **-60 min, 1, 2, 3, 4, 5, 6, 7, 8, 9, 10, 23, 24, 25 h**

Washout period at least 1 week

Study Session 3**[Procedure Day 5 and 6]**

Product: **Metronidazole cream, 0.75% (generic)**
Time of admission: **Morning of Procedure Day 5**
Time of application: **Morning of Procedure Day 5**
Duration of application: **25 h**
Sampling: **26 hours**
Sampling time points: **-60 min, 1, 2, 3, 4, 5, 6, 7, 8, 9, 10, 23, 24, 25 h**

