3 OBJECTIVES

3.1 Study Objectives

- 1) Generate human PK data by collecting data following the application of three metronidazole formulations: RLD and generic metronidazole gel, 0.75% and generic metronidazole cream, 0.75%. This data will be used to assess the bioequivalence of these products or lack thereof.
- 2) To develop in vitro/in vivo correlation (IVIVC) models for dermal products. PK data from this study as well as in vitro data collected elsewhere from IVPT studies will be used to develop IVIVC models which could provide a surrogate for conducting clinical endpoint studies (required to demonstrate bioequivalence of dermal products).

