5 PHARMACOKINETICS AND STATISTICAL CONSIDERATIONS

5.1 Analyses

Metronidazole concentrations will be measured in serum samples collected from each subject. Blood samples (approximately 5 mL (1 tsp)) will be collected during each study session within -60 min prior to gel or cream application and then at 1 h, 2 h, 3 h, 4 h, 5 h, 6 h, 7 h, 8 h, 9 h, 10 h, 23 h, 24 h and 25 h post-application. Non compartmental analyses (NCA) will be conducted to estimate the PK parameters such as: maximum serum concentration (C_{max}) and AUC of the serum concentration–time determined by the linear trapezoidal method. All NCA analyses will be conducted using Phoenix® WinNonlin® 6.4 (Pharsight, a Certara Company, CA).

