5.2 Final Analysis Plan

The objective of this study is to determine PK parameters (C_{max} , AUC) of metronidazole in healthy adults after using metronidazole 0.75% gels or cream.

Student's t-test or Analysis of variance (ANOVA) followed by post-hoc Bonferroni test will be used, where appropriate, for comparing the differences in the means of the PK parameters and significant differences will be declared at $p < 0.05$.

If metronidazole PK concentrations are found to be non-normally distributed, then we will examine Box-Cox transformations (e.g., log, square-root, etc.) that can achieve normality. If no transformation can achieve normality, then will use permutation tests to compute empirical p -values, and will use the bootstrap to compute standard errors and confidence intervals that account for within-person correlation.

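### All 12 subjects get RLD gel, generic gel and cream in the same written order, so product cannot be separated from session

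*Combined protocol and SAP*

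**What the plan says.** The Description of Study Design in the Protocol Summary states: "The study will be an open-label, crossover study over 10 weeks (n=12 healthy subjects) with one week washout period between studies". The same entry then attaches one product to each session. The first is "Procedure Day 1: RLD topical gel containing 0.75% metronidazole to be applied for 25 h". Generic gel is given on Procedure Day 3. Procedure Day 5 is "Generic topical cream containing 0.75% metronidazole to be applied for 25 h". The Schematic of Study Design repeats this order as Study Sessions 1, 2 and 3 under a single n=12 label, with a washout of at least one week between sessions.

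Randomisation, sequence groups and counterbalancing are mentioned nowhere in the documents. Section 5.2 plans a Student's t-test or "Analysis of variance (ANOVA) followed by post-hoc Bonferroni test will be used, where appropriate", with no period or sequence term.

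On the use of the data, section 3.1 says: "This data will be used to assess the bioequivalence of these products or lack thereof". They also feed the IVIVC models. The Objective in the Protocol Summary gives the cream a specific role: "The metronidazole cream, 0.75% will be used as an inequivalent control for the study".

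**The concern.** A crossover removes stable differences between subjects. It removes differences between sessions only if products are spread over sessions. Here every subject has the RLD gel first, the generic gel second and the cream third, so a comparison of products is also a comparison of sessions. A change in application technique, or in skin that has been treated before, would look exactly like a product difference. Assay batch and season would do the same if they follow session, which the documents do not say.

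Both uses of the data are exposed. A session effect could make the two gels look different when they are not. It could also mask or exaggerate the difference between the RLD and the cream, which is always last and is the contrast meant to show that the method can detect inequivalence. The same biased ratios would go into the IVIVC.

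**Working it through.** The plan gives no power, CV, session effect or equivalence limits, so there is no figure of its own to reproduce. The structural result in steps 1 and 2 uses only the documents. Steps 3 to 5 are illustrations on stated assumptions.

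**1. Estimability in the written order.** Twelve subjects in 3 sessions give 36 observations. The model has 12 subject, 2 period and 2 product columns, 16 in all. With one order for everyone, the product columns equal the period columns, so the rank is 14. Neither period contrast can be estimated alongside product, and adding a period term to section 5.2 would not help.

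**2. Size of the bias.** On the log scale,

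estimated product ratio = true ratio × (effect of its session ÷ effect of the comparator's session).

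An effect common to all sessions cancels; a difference between sessions passes through whole. If each session reads 1.10 times the one before and the products are identical, generic gel/RLD is estimated at 1.10 and cream/RLD at 1.10 × 1.10 = 1.21. The sample size does not appear in the expression, so a larger trial gives a narrower interval around the same wrong value.

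**3. Effect on the t-test (assumed CVs and session ratios).** σ_w = √ln(1 + CV²); SE = σ_w × √(2/12); two-sided paired test at 0.05 with 11 df; rejection rate from the noncentral t with noncentrality ln(apparent ratio)/SE. For example, at CV 20%, σ_w = 0.198 and SE = 0.0809; an apparent ratio of 1.20 gives ln(1.20)/0.0809 = 2.26 and a rejection rate of 54%. In the last two rows the session ratio is session 3 to session 1, so the apparent ratio with +10% is 0.80 × 1.10 = 0.88.

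| Chance of declaring a difference | CV 15% | 20% | 30% | 40% |
|---|---|---|---|---|
| Identical products, session ratio 1.10 | 30% | 19% | 11% | 9% |
| Identical products, session ratio 1.20 | 78% | 54% | 28% | 19% |
| Cream truly 0.80 of RLD, no session effect | 91% | 71% | 40% | 25% |
| Cream truly 0.80 of RLD, session ratio 1.10 | 48% | 30% | 16% | 12% |

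The first two rows should read 5%.

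**4. Effect on an equivalence test.** Section 5.2 contains no equivalence test; two one-sided tests with 80–125% limits are assumed here because section 3.1 has a bioequivalence aim. Again n=12 and 11 df.

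| Chance of passing | CV 15% | 20% | 30% | 40% |
|---|---|---|---|---|
| True ratio 0.80, no session effect | 5.0% | 5.0% | 3.3% | 1.0% |
| True ratio 0.80, session ratio 1.10 | 43.0% | 28.7% | 9.6% | 2.0% |
| True ratio 1.00, no session effect | 92.5% | 65.3% | 16.1% | 2.8% |
| True ratio 1.00, session ratio 1.10 | 62.6% | 41.5% | 12.1% | 2.3% |

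The effect is large at low CV and negligible at 40%.

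**5. Sensitivity.** Using 22 df instead of 11 changes any rate in the two tables by at most about 4 percentage points. With Bonferroni for three comparisons (0.05/3 = 1.7%, 22 df), identical products are declared different in 18/10/5/4% of trials at a session ratio of 1.10 and in 66/39/17/10% at 1.20. Detection of a cream at 0.80 falls from 85/57/26/14% to 33/18/8/5% with +10%.

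**6. Balanced alternative.** Six sequences with two subjects each give rank 16 of 16, so period and product are both estimable. The variance of a product contrast is (2/12)σ_w² = 0.167σ_w², the same as in the fixed order without a period term. Residual df are 36 − 16 = 20, against 36 − 14 = 22.

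**The case against.** The strongest reply is that a crossover normally has several sequences, and that the two places may only be listing products by session. The text supplied ends at section 5.2 and has no section on study procedures, so actual conduct may differ. This limits the point to what is written. But both places assign products to named days, neither gives a second order, and a site that follows the text would dose everyone alike.

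Second, no session effect is documented. Application time, duration and sampling are the same in each session, a washout of at least a week separates them, and re-use of the same skin site is not stated. This stands as far as size is concerned: it is unknown. The washout addresses carryover, and residual serum drug can be checked in the sample taken "during each study session within -60 min prior to gel or cream application". Neither deals with other differences between sessions, and data in this layout could never show that such differences are absent.

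Third, the rates depend on the analysis. Section 5.2 does not say that the t-test is paired, offers Bonferroni as an alternative and contains no equivalence test. That is fair. Bonferroni lowers the absolute rates, but against a nominal 1.7% the inflation remains. If the test is run unpaired the rates change and the bias does not. At CVs of 30–40% an equivalence test with 12 subjects would seldom pass anyway (at most 16%), so dosing order would not be the main limitation there.

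**Conclusion.** The concern holds for the plan as written. Product is completely aliased with period, no analysis of fixed-order data can undo it, and any difference between sessions biases the product ratios by its own size. This part rests only on the order stated in the Protocol Summary and the schematic. Whether a session effect exists, and how large it is, cannot be learned from the documents; the rates above depend on assumed CVs, session ratios and limits. Because the first study objective depends on these comparisons, the order must be corrected for any subject not yet dosed and the limitation disclosed for any already dosed.

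**What to change.** Reconcile the crossover label with the order in the Protocol Summary and the schematic. Amend both to randomise subjects not yet dosed to the six sequences of a three-period Williams design, two per sequence if none has been dosed. Products, visits, washout and samples stay as they are. In section 5.2, specify a model with sequence, subject within sequence, period and product. For any subjects dosed in the fixed order, state there that their product contrasts are confounded with period.

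If no one has been dosed, the cost is a randomisation list, an amendment and two residual df (20 instead of 22), with no added subjects, visits or samples. This is Version 7.0 and the documents do not say whether dosing has begun. If some subjects have been dosed, two per sequence over all 12 is no longer possible. For example, with 6 already dosed in the fixed order and the other 6 taking one sequence each, the rank is still 16, but the contrast variance factor is 0.222 instead of 0.167 (0.222/0.167 = 1.33, or 33% larger). That analysis also assumes the same period effects in both groups. If all 12 have been dosed, only the statement of the limitation remains.

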1 KEY ROLES

U01 Principal Investigators:

[name] (contact), PhD, RPh (*PI*)
Professor
Department of Pharmaceutical Sciences
University of Maryland School of Pharmacy
[name]
[name]
[contact]
[contact]
Email: [contact]

Medically Accountable Investigators

[name] MD, MS (*primary*)
Professor
Department of Medicine and Epidemiology (*secondary*)
University of Maryland School of Medicine
[name]
[name]
[contact]
[contact]
E-mail: [contact]

[name]. (*secondary*)
University of Maryland School of Medicine
Department of Medicine
Pediatrics
North Hospital
[name]
[contact] or [contact]
Email : [contact]

Schematic of Study Design**n=12 subjects****Study Session 1****[Procedure Day 1 and 2]**

Product: **Metronidazole gel, 0.75% (RLD)**
Time of admission: **Morning of Procedure Day 1**
Time of application: **Morning of Procedure Day 1**
Duration of application: **25 h**
Sampling: **26 hours**
Sampling time points: **-60 min, 1, 2, 3, 4, 5, 6, 7, 8, 9, 10, 23, 24, 25 h**

Washout period at least 1 week

Study Session 2**[Procedure Day 3 and 4]**

Product: **Metronidazole gel, 0.75% (generic)**
Time of admission: **Morning of Procedure Day 3**
Time of application: **Morning of Procedure Day 3**
Duration of application: **25 h**
Sampling: **26 hours**
Sampling time points: **-60 min, 1, 2, 3, 4, 5, 6, 7, 8, 9, 10, 23, 24, 25 h**

Washout period at least 1 week

Study Session 3**[Procedure Day 5 and 6]**

Product: **Metronidazole cream, 0.75% (generic)**
Time of admission: **Morning of Procedure Day 5**
Time of application: **Morning of Procedure Day 5**
Duration of application: **25 h**
Sampling: **26 hours**
Sampling time points: **-60 min, 1, 2, 3, 4, 5, 6, 7, 8, 9, 10, 23, 24, 25 h**

2 BACKGROUND INFORMATION AND SCIENTIFIC RATIONALE

2.1 Background Information

Generic drugs are approved based upon bioequivalence (BE) testing, and with respect to oral drug delivery, the accepted BE approach is relatively straightforward and is principally based on matching blood level profiles. In some cases, in vitro dissolution tests can be done to help determine the bioequivalence of an oral dosage form. For topical drug products in the United States, with the exception of corticosteroids and a few other products, a comparative clinical endpoint study is often necessary for approval of a generic product or for replacement of an approved dermatological drug product with one that has major changes. Comparative clinical trials are relatively insensitive, time-consuming and costly. It is especially difficult to gain the adequate statistical power needed to evaluate bioequivalence for some dermatological conditions, and can require a large number (i.e., hundreds^{1,2}) of subjects.

This study supports FDA's continuing effort to identify the most accurate, sensitive, reproducible and efficient methods to evaluate topical dermatological drug products.

The model drug for this study is metronidazole, which is available in different topical formulations, gel, cream and lotion, approved by the United States FDA. The metronidazole gels and cream have been chosen for this study because the therapeutically equivalent metronidazole gels will be used to evaluate BE in vivo. The metronidazole cream is being used as the non-BE control for this project.

2.2 Rationale

The goal of this study is to help establish more efficient pathways for approval of topical drug products by developing better tools to assess bioavailability. This study with a RLD and generic metronidazole topical gel, 0.75% and generic metronidazole topical cream, 0.75% will provide sufficient systemic concentrations of metronidazole to characterize the systemic bioavailability. The same products will also be studied (under a parallel but separate in vitro study protocol) using an in vitro permeation test (IVPT) model with excised human skin. The IVPT model has demonstrated IVIVC in previous studies using different drug molecules and formulations. This research will help establish whether the IVPT model correlates with and is predictive of in vivo bioavailability, and whether IVPT can be utilized as part of a collective weight-of-evidence approach to support an approval pathway for topical drug products.

These coordinated evaluations also collectively provide the in vivo reference datasets that are needed to establish IVIVC for the IVPT model which may then be utilized to support a new pathway for approval of numerous topical drug products for patients.

Metronidazole topical products

	Metronidazole gel, 0.75% (RLD) NDC: 66993-962-45	Metronidazole gel, 0.75% (generic) NDC: 0115-1474-46	Metronidazole cream, 0.75% (generic) NDC: 0168-0323-46
Inactive ingredients	0.8 mg of methylparaben and 0.2 mg of propylparaben as preservatives in a gel consisting of carbomer 940, edetate disodium, propylene glycol, purified water and sodium hydroxide	Carbopol 980, edetate disodium, methylparaben, propylene glycol, propylparaben, purified water and sodium hydroxide	Emulsifying wax, sorbitol solution, glycerin, isopropyl palmitate, benzyl alcohol, lactic acid, sodium hydroxide and purified water
Formulation	topical gel	topical gel	topical cream
Manufacturer	Prasco Laboratories	Impax Generics	Fougera Laboratories

3 OBJECTIVES

3.1 Study Objectives

- 1) Generate human PK data by collecting data following the application of three metronidazole formulations: RLD and generic metronidazole gel, 0.75% and generic metronidazole cream, 0.75%. This data will be used to assess the bioequivalence of these products or lack thereof.
- 2) To develop in vitro/in vivo correlation (IVIVC) models for dermal products. PK data from this study as well as in vitro data collected elsewhere from IVPT studies will be used to develop IVIVC models which could provide a surrogate for conducting clinical endpoint studies (required to demonstrate bioequivalence of dermal products).

3.2 Study Outcome Measures

For the PK study the main outcome measure is the maximum serum concentration (C_{max}), time of maximum serum concentration (T_{max}) of metronidazole and area under the curve (AUC) attained from RLD and generic metronidazole gel, 0.75% and generic metronidazole cream, 0.75%.

4 STUDY ENROLLMENT AND WITHDRAWAL

4.1 Subject Inclusion Criteria

Subjects are eligible for this study if they fulfill the inclusion criteria specified below:

1. Men or non-pregnant, women who are of any ethnic background between the age of 18 and 45 years old.
2. Subjects must be non-smokers/tobacco users (must have refrained from the use of nicotine-containing substances (e.g., cigarettes, cigars, chewing tobacco, snuff, gum, patches or electronic cigarettes) over the previous 2 months and are not currently smoking/using tobacco products.
3. Provide written informed consent before initiation of any of the study procedures.
4. Agree not to participate in another clinical trial/study during the study period or to participate in an investigational drug study for at least 1 month after the last study session.
5. Able to adhere to the study protocol schedule and study restrictions.
6. Able to participate in all study sessions.
7. Subjects have upper arms large enough to allow for the placement of 200 cm² [31 in²] area for application of gels or cream.
8. Subjects deemed to be healthy as judged by the Medically Accountable Investigator (MAI) and determined by medical history, physical examination and medication history.
9. Negative urine drug screening test (cannabinoids, amphetamines, barbiturates, benzodiazepine, cocaine, methadone, opiates, PCP).
10. Have normal screening laboratories for WBC, Hgb, platelets, sodium, potassium, chloride, bicarbonate, BUN, creatinine, ALT and AST.
11. Have normal screening laboratories for urine protein and urine glucose.
12. Female subjects must be of non-childbearing potential (as defined as surgically sterile [i.e. history of hysterectomy or tubal ligation] or postmenopausal for more than 1 year), or if of childbearing potential must be non-pregnant at the time of enrollment and on the morning of each procedure day, and must agree to use reliable hormonal or barrier birth control such as implants, injectables, combined

-
- oral contraceptives, some intrauterine devices (IUDs), sexual abstinence, or a vasectomized partner.
13. Agrees not to donate blood to a blood bank throughout participation in the study and at least 3 months after the last study session.
 14. Have a normal ECG; must not have the following to be acceptable: pathologic Q wave abnormalities, significant ST–T wave changes, left ventricular hypertrophy, right bundle branch block, left bundle branch block. (sinus rhythm is between 55–100 beats per minute).
 15. Have normal vital signs:
 - Temperature 35-37.9°C (95-100.3°F)
 - Systolic blood pressure 90-165 mmHg
 - Diastolic blood pressure 60-100 mmHg
 - Heart rate 55-100 beats per minute
 - Respiration rate 12-20 breaths per minute

